3.2. Study Population

Healthy volunteers aged 18-50 years (male or non-pregnant females) who are seronegative for previous SARS-CoV-2 infection (no anti-N SARS-CoV-2 responses or history of exposure). All groups will be recruited and vaccinated at the NIHR CRF, Southampton. Only subjects who meet all inclusion criteria and none of the exclusion criteria (specified in **Section 4**) will be allowed to participate in this study. The selection criteria include adequate provisions to minimize the risk and protect the well-being of subjects in the study.

3.3. Description of Study Cohorts

There will be up to study groups in the trial, with a total of up to 36 volunteers.

Stage 1	Group 1a	6 volunteers; 2 doses of pEVAC-PS at 0.2mg intradermally on Day 0 and Day 28.
	Subgroup 1a- expanded	12 volunteers; 2 doses of pEVAC-PS at 0.2mg intradermally on Day 0 and Day 28.
Stage 2	Group 2a	9 volunteers; 2 doses of pEVAC-PS at 0.4mg OR 0.8mg intradermally on Day 0 and Day 28.
	Group 2b	9 volunteers; 2 doses of pEVAC-PS at 0.8mg OR 1.2mg intradermally on Day 0 and Day 28.
	Group 2c If the target is not met from group 2a or 2b (0.8mg)	12 volunteers; 2 doses of pEVAC-PS 1.2mg intradermally on Day 0 and Day 28
Stage 3	Group 3 If primary immunogenicity target is met during Stage 2	12 volunteers; 2 doses of pEVAC-PS at the most well tolerated and immunogenic dose from Group 2a or 2b on Day 0 and Day 28.
	If the immunogenicity targets are not met by 1.2mg in group 2b, no further participants will be enrolled.	

Table 1: Study groups.

Figure 1. Study Flow Diagram

3.4 Number of Volunteers/Centres

The study will be conducted at one UK site, Southampton NIHR Clinical Research Facility. The target is to enrol up to 36 healthy volunteers (female and/or male).

3.5. Dose escalation

The sentinel participant in each group will be observed for 1 hr post vaccination for any local reactions and contacted 24hrs afterwards by the medical team to review symptoms and check against symptom diary. If no safety concerns are identified (section 7.9.1), the subsequent 5 participants can be vaccinated a minimum of 1 hour apart. Each participant will be observed for 60 minutes post vaccination. After review of participants at 72hrs post dosing, if no stopping criteria have been met (section 7.9) then the procedure can be repeated with the first subject at the next dose level.

3.5.1. Rationale and Design of Dose optimisation Strategy

Current formulation constraints mean that the minimum dose of pEVAC-PS which can be administered intradermally is 0.2mg, and the maximum is 1.2mg. An adaptive protocol allows optimisation within this dosing range with potential to expand groups which achieve desirable immunogenicity and reactogenicity profiles.

Sufficient immune responses are expected from significantly lower doses administered intradermally given the increased numbers of antigen presenting cells present within the dermis as compared to muscle cells.

The adaptive design from intradermal administration starts at the lowest currently achievable dose. If that is successful, this dosing group will be expanded, and the team will review the potential for additional groups receiving lower doses (this will require adaptation of the formulation).

If primary immunogenicity endpoints are not met, successive groups will be enrolled at higher doses until the pre specified immunogenicity target is met. At this point, the group with the optimum immunogenicity and reactogenicity profile will be further expanded.

4. Participant Eligibility Criteria

4.1. Inclusion Criteria

The healthy adult volunteers must meet all the following inclusion criteria to be eligible for the study:

- Healthy adults aged 18-50 years.
- Able and willing (in the Investigator's opinion) to comply with all study requirements (participants must not rely on public transport or taxis).
- Willing to allow the investigators to discuss the volunteer's medical history with their General Practitioner and access all medical records when relevant to study procedures.

- Agreement to refrain from blood donation during the course of the study.
- Provide written informed consent.
- Completed a 2 dose primary immunisation course against COVID-19, with the most recent dose administered no less than 12 weeks (84 days) previously

Female volunteers of childbearing potential are required to use an effective form of contraception at enrolment and until after 3 months following their last personal dose of vaccination within the study. A woman of childbearing potential is defined as a premenopausal female who is capable of becoming pregnant. Menopause can be diagnosed in a woman aged over 50 after one year of amenorrhoea (this applies only if the woman is not using hormonal contraception).

Acceptable forms of contraception for female volunteers are as follows:

- Established use of oral, injected or implanted hormonal methods of contraception
- Placement of an intrauterine device or intrauterine system
- Total abdominal hysterectomy or surgical sterilisation
- Barrier methods of contraception (condom or occlusive cap with spermicide)
- Male sterilisation if the vasectomised partner is the sole partner for the subject
- True abstinence when this is in line with the preferred and usual lifestyle of the subject

4.2 Exclusion criteria

The volunteer may not enter the study if any of the following apply:

- History of laboratory confirmed MERS, SARS-CoV-1 or SARS-CoV-2 infection
- Seropositive for SARS-CoV-2 Nucleocapsid IgG at screening
- Have an anti-SARS-CoV-2 and a SARS-CoV-1 RBD response of more than 2 AUC (Area Under the Curve) units
- Planned receipt of any vaccine other than the study intervention within 30 days before and after each study vaccination.
- Administration of immunoglobulins and/or any blood products within the three months preceding the planned administration of the vaccine candidate.
- Any confirmed or suspected immunosuppressive or immunodeficient state, including HIV infection; asplenia; recurrent severe infections and use of immunosuppressant medication within the past 6 months, except topical steroids or short-term oral steroids (course lasting <14 days).
- Any autoimmune conditions, except mild psoriasis, well-controlled autoimmune thyroid disease, vitiligo or stable coeliac disease not requiring immunosuppressive or immunomodulatory therapy.
- History of allergic disease or reactions likely to be exacerbated by any component of the pEVAC-PS vaccine
- Any history of angioedema.
- Any history of anaphylaxis.
- Pregnancy, lactation or willingness/intention to become pregnant for 3 months following the last personal dose of vaccine in this trial.

- History of cancer (except basal cell carcinoma of the skin and cervical carcinoma in situ).
- History of serious psychiatric condition likely to affect participation in the study (e.g. ongoing severe depression, history of admission to an in-patient psychiatric facility, recent suicidal ideation, history of suicide attempt, bipolar disorder, personality disorder, alcohol and drug dependency, severe eating disorder, psychosis, use of mood stabilisers or antipsychotic medication).
- Bleeding disorder (e.g. factor deficiency, coagulopathy or platelet disorder), or prior history of significant bleeding or bruising following IM injections or venepuncture.
- Any other serious chronic illness requiring hospital specialist supervision.
- Chronic respiratory diseases, including mild asthma (resolved childhood asthma is allowed)
- Chronic cardiovascular disease (including hypertension), gastrointestinal disease, liver disease (except Gilberts Syndrome), renal disease, endocrine disorder (including diabetes) and neurological illness (excluding migraine)
- Seriously overweight (BMI≥40 Kg/m²) or underweight (BMI≤18 Kg/m²)
- Suspected or known current alcohol abuse as defined by an alcohol intake of greater than 42 units every week.
- Suspected or known injecting drug abuse in the 5 years preceding enrolment.
- Any clinically significant abnormal finding on screening biochemistry, haematology blood tests or urinalysis.
- Any other significant disease, disorder or finding which may significantly increase the risk to the volunteer because of participation in the study, affect the ability of the volunteer to participate in the study or impair interpretation of the study data.

5. Conduct of the study

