5.2 Schedule of events

Table 2. Schedule of events

Attendance Number	1 ^s	2	3	4	5	6	7	8	9	10	11	12 [†]	COVID-19 Testing
Timeline** (days)	≤90	0	1	3	7	14	28	42	56	84	182	365	As required
Time window (days)				±1	±2	±3	±7	±3	±7	±3	±14	± 28	N/A
Informed Consent	Х												
Review eligibility criteria	Х	х					Х						
Vaccination (IM)		Х					Х						
Vital signs^	Х	Х		Х	Х	Х	Х	Х	Х	Х	Х	Х	х
Height and weight	Х												
Telephone/Video call			Х										
Ascertainment of adverse events and con meds		Х	Х	Х	Х	Х	Х	Х	Х	Х	Х	Х	Х
Diary cards provided		Х					Х						
Diary cards reviewed			Х	Х	Х	Х	Х	Х	Х				
Medical History, Physical Examination	Х	(X)		(X)	(X)	(X)	(X)	(X)	(X)	(X)	(X)	(X)	(X)
Biochemistry, Haematology (mL)	5	5		5	5		5	5					5
Exploratory immunology (mL)		50			50	50	50	50	50	50	50	50	up to 50
Nose/Throat Swab													Х
Urinalysis	х												
Urinary bHCG (women only)	Х	Х					х						
HBsAg, HCV Ab, HIV serology (mL)	5												
Blood volume per visit	10	61.5		5	55	50	55	55	50	55	50	50	up to 57.5
Cumulative blood volume [%]	10	71.5		76.5	131.5	181.5	236.5	291.5	341.5	396.5	446.5	496.5	554

S=screening visit; (X) = if considered necessary ^ = Vital signs includes pulse, blood pressure and temperature; ** Timeline is approximate only. Exact timings of visits relate to the day on enrolment, i.e., each visit must occur at indicated number of days after enrolment ± time window. % Cumulative blood volume for volunteers if blood taken as per schedule, and excluding any repeat safety blood test that may be necessary. [†]Only for the final group which are enrolled

.

Table 3: Schedule of Events for Unscheduled and Early Termination Visits. Applicable for

 both all groups

	Unscheduled Visit Following AE	Early Termination Visit
Medical History	(x)	(x)
Physical Examination	(X) ¹	(x)
ECG	(x)	
Urinalysis	(x)	
Physical Observations	х	х
Concomitant medications	х	х
AEs reviewed	х	х
Diary card review ²	х	(x)
Haematology (mL)	3	3
Biochemistry (mL)	5	5
Coagulation (mL)	(2.7)	(2.7)

(x) = If considered necessary, emphasising any acute complaints.

¹ A full physical examination or symptom directed physical examination can be carried out at the discretion of the investigator.

² Required if the participant is currently within the diary card completion phase of the study only.

The above schedule is not an exhaustive list; procedures carried out will be guided by clinical need and will be at the discretion of the investigator.

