5.3.5. Blood Tests

Blood will be drawn for the following laboratory tests and processed:

1. At University Hospital Southampton NHS Foundation Trust Laboratories, using NHS standard procedures:

- Haematology; Full Blood Count.
- **Biochemistry;** Sodium, Potassium, Urea, Creatinine, Albumin, Liver Function, Magnesium and Cholesterol.
- **Diagnostic serology;** HBsAg, HCV antibodies, HIV antibodies (specific consent will be gained prior to testing blood for these blood-borne viruses).
- β-HCG serum (female volunteers only)

2. At LVZ laboratories:

Immunology: Serological analysis of antibody responses (such as ELISA); B cell assays. Other immunological assays including flow cytometry, pseudotype neutralisation for Sarbeco viruses, amongst others, and T-cell assays may be performed at the discretion of the Investigators.

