5.4.2. Screening Clinical Assessments

No trial specific procedure should be carried out prior to signing the consent form for this study. All potential volunteers will have a screening visit, which may take place up to 90 days prior to vaccination. Informed consent will be taken before screening, as described in **section 5.4.1**. If consent is obtained, the procedures indicated in the schedule of events will be undertaken including a medical history, physical examination, blood tests, and urine test. To avoid unnecessary additional venepuncture, if the appropriate blood test results for screening are available for the same volunteer from a screening visit for another study, these results may be used for assessing eligibility (provided the results date is within the 3 months preceding administration of the first dose of pEVAC-PS).

Abnormal clinical findings from the medical history, physical examination and all tests at screening will be assessed by a clinician referring to site-specific laboratory adverse event grading tables which are filed in the trial master file (TMF). Any abnormal test result deemed clinically significant may be repeated to ensure it is not a single occurrence. If an abnormal finding is deemed to be clinically significant, the volunteer will be informed and appropriate medical care arranged with the permission of the volunteer.

The eligibility of the volunteer will be reviewed by the study clinician at the end of the screening visit and again when all results from the screening visit have been considered and a copy of the volunteer's medical history has been received from the GP. Decisions to exclude the volunteer from enrolling in the trial or to withdraw a volunteer from the trial will be at the discretion of the Investigator. If eligible, a day 0 visit will be scheduled for the volunteer to receive the vaccine.

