5.5.3 Participants under quarantine

Given the evolving epidemiological situation both globally and in the UK, should a participant be under quarantine and unable to attend any of the scheduled visits, a telephone/video consultation will be arranged using smartphone or computer app if clinically appropriate in order to obtain core study data where possible.

Participants with confirmed SARS-CoV-2 infection (COVID-19 Pathway)

Participants will be counselled at enrolment that should they receive a positive SARS-CoV-2 test (e.g. an antigen detection or nucleic acid amplification test, for example, via test and trace or occupational health services) they should contact the trial team on receipt of the positive result. A study doctor will be available to direct the volunteer for routine medical care via standard NHS pathways should that be appropriate, depending on the volunteer's clinical condition.

This COVID-19 pathway will apply to participants tested via symptomatic and asymptomatic pathways.

Once the participant has conveyed their result to the study team, and the study team confirm an appropriate test has been used (verbal discussion with participant as to how testing was obtained, confirmatory documentation will not be sought), an appointment will be arranged to review the participant. At this visit blood samples for safety (FBC, Biochemistry, CRP and others if deemed clinically relevant) and immunology (PBMCs and serum for cellular and humoral immune responses) will be taken, along with a nasopharyngeal swab for storage and subsequent viral isolation. Vital signs and other clinical data will be recorded.

Participants will be eligible if they can attend the site for a COVID-19 visit within 7 days of a positive test.

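### The N IgG and RBD eligibility tests are missing from the screening schedule, and the dose-decision rule can score an undetected SARS-CoV-2 infection as a vaccine response

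*Protocol*

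**What the plan says.** **Eligibility.** Section 4.2 excludes a volunteer who is "Seropositive for SARS-CoV-2 Nucleocapsid IgG at screening". A separate criterion reads "Have an anti-SARS-CoV-2 and a SARS-CoV-1 RBD response of more than 2 AUC (Area Under the Curve) units" and names no time point.

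**Screening tests.** Table 2 (section 5.2) gives the screening visit 5 mL for biochemistry and haematology and 5 mL for blood-borne virus serology, 10 mL in total. The immunology row is empty at screening and starts with 50 mL on Day 0. The diagnostic serology in section 5.3.5 is "HBsAg, HCV antibodies, HIV antibodies"; anti-N is not listed there. Section 5.8.2, on labelling samples for the serology laboratory, gives S as an example of a study-day label.

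**Timing.** Section 5.4.2 says of the screening visit, "which may take place up to 90 days prior to vaccination". Eligibility is reviewed again on Day 0 and Day 28 (Table 2, section 5.5.1), with no N or RBD assay attached.

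**Infection after enrolment.** Under section 5.5.3 participants are asked to tell the team about a positive test. "This COVID-19 pathway will apply to participants tested via symptomatic and asymptomatic pathways", but the pathway starts with that report.

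**Decision rule.** Section 3.1.1 decides on the proportion of each group that has seroconverted, 8 weeks after dose 1. A positive RBD ELISA for SARS-CoV, SARS-CoV-2 or both qualifies, and responders are counted as 2-fold titre rises. The thresholds are 5 of 6 (Stage 1), 7 of 9 (Groups 2a and 2b) and 10 of 12 (expanded Group 1). Nothing is said about participants infected in the interval.

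**The concern.** The protocol admits only people without evidence of past infection, so it already treats infection as something that would confuse the antibody readout. That control weakens in two places. The tests that establish the status are not in the schedule, and the status is not checked again between screening and the Day 56 readout.

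The dose path is then chosen from a count in 6, 9 or 12 people with no control arm. A natural infection can raise SARS-CoV-2 RBD antibody, which by itself satisfies the responder definition. If it is asymptomatic or unreported, nothing in the trial would show that the rise did not come from the vaccine. At stake is a dose expanded, or not escalated, because of a response that the vaccine did not cause.

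**Working it through.** **1. Screening blood volume (Table 2).** 5 (biochemistry, haematology) + 5 (HBsAg, HCV, HIV) + 0 (immunology) = 10 mL, equal to the stated 10 mL. The itemised rows leave no volume for N or RBD serology.

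The table is not fully reliable as an inventory, however:
- Day 0: 5 + 50 = 55 mL against 61.5 stated.
- Day 84: 50 mL against 55 stated.
- COVID-19 visit: 5 + 50 = 55 mL against 57.5 stated.
- Serum β-HCG at screening (5.3.5, 5.3.7) has no row.

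**2. Could the Day 0 draw settle eligibility?** Not as written. Section 5.8.4 has it couriered to the outside laboratory or frozen and batched, and tested only after written sponsor approval for the batch. No result before dosing is provided for.

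**3. Effect on the decision.** The documents give neither an infection risk nor an expected response rate, so both are assumptions:
- q = risk of infection from Day 0 to Day 56: 2%, 5%, 10%, 20%.
- p = true vaccine response rate: 0.6 in the main case.
- Every infected participant is scored as a responder (the worst case).

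Apparent response rate: e = p + (1 − p)q. For p = 0.6 and q = 0.10, e = 0.6 + 0.4 × 0.10 = 0.64.

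P(≥5 of 6) = 6e⁵(1 − e) + e⁶. At e = 0.6: 0.1866 + 0.0467 = 0.233.

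P(≥7 of 9) = 36e⁷(1 − e)² + 9e⁸(1 − e) + e⁹. At e = 0.6: 0.1612 + 0.0605 + 0.0101 = 0.232.

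| q | e | P(≥5/6) | P(≥7/9) | P(≥10/12) |
|---|---|---|---|---|
| 0 | 0.600 | 0.233 | 0.232 | 0.083 |
| 2% | 0.608 | 0.246 | 0.247 | 0.092 |
| 5% | 0.620 | 0.266 | 0.271 | 0.107 |
| 10% | 0.640 | 0.301 | 0.314 | 0.135 |
| 20% | 0.680 | 0.378 | 0.411 | 0.208 |

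For the 5/6 and 7/9 rules the rise is 1 to 4 percentage points at 2–5% infection and 7 to 18 points at 10–20%.

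**4. One infection in Stage 1.** If exactly one of six is infected and scored as a responder, 4 of the other 5 suffice. The chance of meeting the target goes from 0.233 to 0.337 at p = 0.6, and from 0.109 to 0.188 at p = 0.5.

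**5. Inactive vaccine (p = 0).** Infection alone gives P(≥5/6) of at most 0.002, even at q = 20%. The chance of landing in the middle class (3 or 4 of 6) instead of the poor-response class is 0.016 at q = 10% and 0.097 at q = 20%.

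**6. Chance of any infection, 1 − (1 − q)ⁿ.** For n = 6: 0.114, 0.265, 0.469, 0.738. For n = 9: 0.166, 0.370, 0.613, 0.866. These show how often the question would arise, not how often a decision would change. A change needs the infected person to be an otherwise non-responder and the count to sit just below the threshold.

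Infection between screening and Day 0 is not in this arithmetic. It breaks the population definition, and its effect on a fold rise from baseline could go either way.

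**The case against.** Three stronger readings are tempting, and the documents do not support them.

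*No screening sample is taken for these tests.* A missing row does not prove this. The label S in 5.8.2 suggests that a screening sample reaches the serology laboratory, serum β-HCG shows that Table 2 omits at least one required screening test, and several volumes in the table do not add up. This is an inconsistency to reconcile. It is still one that the schedule and assay list must settle, because those belong to the protocol.

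*Boosted participants count at the Day 56 decision.* Section 4.2 excludes "Planned receipt of any vaccine other than the study intervention within 30 days before and after each study vaccination". With dose 2 on Day 28 this runs to 28 + 30 = Day 58, after the readout. Only the extremes of the visit windows leave a gap: dose 2 on Day 21 bars other vaccines to Day 51, and the readout may fall on Day 63. Boosters before the Day 84, 182 and 365 samples are possible, but the SAP, not shown here, can say how those titres are handled.

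*Infected participants stay in the final immunogenicity analysis.* Section 8.2 makes that analysis per protocol, and the set may be defined in the SAP. The silence matters for the 3.1.1 count, which nothing ties to that set.

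It is also fair that known infections are visible. Laboratory-confirmed infection is an exclusion re-checked on Day 0 and Day 28, infection is an adverse event of special interest (7.4), withdrawal and replacement are provided for (5.6, 5.6.1), and section 8.1 lets investigators use all available information. All of this depends on the infection being known. None of it reaches an asymptomatic or unreported one. Section 5.3.5 allows serological assays on post-dose serum in general terms, so an N test is feasible, but nothing requires it.

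**Conclusion.** The point holds in this form. The N and RBD tests that section 4.2 relies on are absent from the screening column of Table 2, and N is absent from 5.3.5. No N test is repeated over a span of up to 90 days before dose 1 plus 56 days after it. Followed as written, section 3.1.1 scores an undetected infection as a vaccine response.

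The size is modest to material. At a true response rate of 0.6 the chance of meeting a 5/6 or 7/9 threshold rises by 1 to 4 points for infection risks of 2–5% and by 7 to 18 points for 10–20%. Both rates are assumptions, and scoring every infection as a response makes these upper figures. The distortion falls on intermediate response rates, where the dose choice is decided; it would not make an inactive vaccine look successful. With no control arm, the trial's own data would not reveal it.

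**What to change.** 1. List N IgG and RBD ELISA in the screening column of Table 2 with their volume, add N IgG to section 5.3.5, give the RBD criterion in 4.2 a time point, and bring 5.8.2 into line.
2. Run N IgG on the Day 0 and Day 56 sera already drawn, before each dose-decision review.
3. State in section 3.1.1 that a participant who is N-positive at Day 0, or who has N seroconversion or confirmed infection between Day 0 and the Day 56 draw, is not evaluable for the responder count. Show the all-participant count beside it as a sensitivity analysis.
4. Say how the thresholds apply when fewer than 6, 9 or 12 are evaluable, or that such participants are replaced under 5.6.1.

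Handling of boosters before the later samples can stay with the SAP.

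The cost is at most a small extra tube at the screening draw, two N assays per participant on serum already collected, and a few sentences of text. The drawback is the occasional loss of an evaluable participant in a small group. N serology will not detect every infection, which is why reported infection stays in the rule.
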